### **6.1.1.3 Adverse Events of Special Interest**

The following AEs of special interest will be monitored during the study (see detailed toxicity management in Section [6.1.7](#)):

- Serious infections
- Opportunistic infections
- Herpes zoster
- Tuberculosis;
- Malignancy (all types);
- Gastrointestinal perforations;
- Adjudicated cardiovascular events (e.g., major adverse cardiovascular event [MACE]);
- Lipid profile changes;
- Anemia;
- Neutropenia;
- Lymphopenia;
- Increased serum creatinine and renal dysfunction;
- Hepatic events and increased hepatic transaminases;
- Elevated creatine phosphokinase (CPK);
- Embolic and thrombotic events (non-cardiac, non-CNS).

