
**Table 7. Specific Toxicity Management Guidelines for Abnormal Laboratory Values (Continued)**

Laboratory Parameter	Toxicity Management Guideline
Serum Creatinine	
 
If serum creatine is <math>> 1.5 \times</math> the baseline value and <math>></math> ULN, repeat the test for serum creatinine (with subject in an euvolemic state) to confirm the results. If the results of the repeat testing still meet this criterion, then interrupt study drug and re-start study drug once serum creatinine returns to <math>\leq 1.5 \times</math> baseline value and <math>\leq</math> ULN.
 
If confirmed serum creatinine <math>\geq 2</math> mg/dL, interrupt study drug and re-start study drug once serum creatinine returns to normal reference range or its baseline value.
 
 
For the above serum creatinine elevation scenarios, complete supplemental renal eCRF.

Creatine Phosphokinase	
 
If confirmed CPK value <math>\geq 4 \times</math> ULN and there are no symptoms suggestive of myositis or rhabdomyolysis, the subject may continue study drug at the investigator's discretion.
 
If CPK <math>\geq 4 \times</math> ULN accompanied by symptoms suggestive of myositis or rhabdomyolysis, interrupt study drug and contact AbbVie TA MD.
 
 
For the above CPK elevation scenarios, complete supplemental CPK eCRF.

For allowed study drug interruption, the following rules apply:

### Period 1

- Allow study drug interruption up to 7 consecutive days for AEs and emergency surgery. Elective surgery will not be allowed during the first 12-week period.
- If the subject must undergo emergency surgery, the study drug should be interrupted at the time of the surgery. Allow reintroduction of study drug once the physician has examined the surgical site and determined that it has healed and there is no sign of infection.

### Period 2

- Allow study drug interruption up to 7 consecutive days for AEs and emergency surgery during Week 12 to Week 24 in Period 2 and after Week 24 and thereafter, up to 30 consecutive days of study drug interruption is allowed.

- If the subject undergoes elective surgery, the study drug should be interrupted 1 week prior to the planned surgery. Allow reintroduction of study drug once the physician has examined the surgical site and determined that it has healed and there is no sign of infection.

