10.3.2.3 Assessment of Potentially Clinical Significant Laboratory Variables

The criteria for potentially clinically significant laboratory values will be determined by OMERACT criteria of Grade 3 or 4. For creatine phosphokinase, creatinine, NCI CTC criteria will be used.

The number and percentage of subjects meeting the criteria for potentially clinically significant laboratory values will be summarized by "as treated" treatment group and overall. Comparisons of the percentage of subjects experiencing a value meeting the criteria between treatment groups will be performed using Fisher's exact tests. Only p-values ≤ 0.100 when rounded to three digits will be presented.

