10.3.3.2 Assessment of Potentially Clinical Significant Laboratory Values

Long term laboratory data will be summarized based on the number and percentage of subjects meeting the criteria for potentially clinical significant laboratory values and by the actual treatment received at the time of the event occurrence. The treatment groups are the same as the ones for long term AE analysis as described in Section 10.2.2. A subject can be counted under different treatment groups if he/she switched treatment and experienced potentially clinical significant laboratory values under different treatment groups.

A listing of all subjects with any laboratory determination meeting OMERACT criteria of Grade 3 or 4 will be provided by Grade. For creatine phosphokinase, creatinine, NCI CTC criteria will be used. For each of these subjects, the whole course of the respective parameter will be listed.

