L8. Hypokalaemia (mg/dl)***	-	3.0 – 3.4	2.5 – 2.9
			> 3.0; or Hgb < 7.0
			< 1.0
			< 0.5
			< 0.5
			< 20; recurrent platelet transfusions required
			> 13.5; or associated coma
			> 500, or associated with ketoacidosis
			> 7.0 or any arrhythmia
			< 6.5 or occurrence of tetany
			< 30 or coma
			< 120
			< 2.5

L. Chemistry (Continued)

L9. CPK (also if polymyositis-disease) ****	> ULN – 1.5 × ULN	> 2.5 – 5.0 × ULN	> 5.0 – 10.0 × ULN	> 10.0 × ULN
L10. Serum uric acid	1.2 – 1.6 × ULN	1.7 – 2.9 × ULN	3.0 – 5.0 × ULN or gout	NA
L11. Creatinine (mg/dl) ***	> 1 – 1.5 × Baseline; > ULN – 1.5 × ULN	> 1.5 – 3.0 × Baseline; > 1.5 – 3.0 × ULN	> 3.0 baseline; > 3.0 – 6.0 × ULN	> 6.0 × ULN
L12. SGOT (AST)	1.2 – 1.5 × ULN	1.6 – 3.0 × ULN	3.1 – 8.0 × ULN	> 8.0 × ULN
L13. SGPT (ALT)	1.2 – 1.5 × ULN	1.6 – 3.0 × ULN	3.0 – 8.0 × ULN	> 8.0 × ULN
L14. Alkaline phosphatase	1.1 – 1.5** × ULN	1.6 – 3.0 × ULN	3.0 – 5.0 × ULN	> 5.0 × ULN
L15. T. bilirubin	1.1 – 1.4 × ULN	1.5 – 1.9 × ULN	2.0 – 3.0 × ULN	> 3.0 × ULN
L16. LDH	1.3 – 2.4 × ULN	2.5 – 5.0 × ULN	5.1 – 10 × ULN	> 10 × ULN
M. Urinalysis				
M1. Haematuria	Micro only	Gross, no clots	Clots, transfusion < 2 units	Transfusion required
M2. Proteinuria (per 24 h)	300 – 500 mg (tr/1+)	501 – 1999 mg (2+)	2 – 5.0 g (3+) nephrotic syndrome	5.0 g (4+) anasarca
M3. WBC in urine	NA	NA	Indicating acute interstitial nephritis	Associated with acute renal failure
M4. Uric acid crystals	Present without symptoms	NA	With stones or symptoms of stones (e.g., renal colic)	Causing renal outflow obstruction and hospitalization

*: in L11, 1.5 – 1.8 × ULN is changed to 1.4 – 1.8 × ULN.

**: in L14, 1.1 – 2.0 × ULN is changed to 1.1 – 1.5 × ULN.

***: in L3, L7 and L8, mg/dl is changed to mmol/l

****: NCI CTC grade

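### Creatinine values that interrupt study drug, and CPK of 4–5 × ULN, can be Grade 2 and so fall outside the SAP's clinically significant counts and long-term listing (minor)

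*SAP*

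**What the plan says.** **Counting rule.** SAP 10.3.2.3: "The criteria for potentially clinically significant laboratory values will be determined by OMERACT criteria of Grade 3 or 4". It adds: "For creatine phosphokinase, creatinine, NCI CTC criteria will be used". The percentages are compared between groups with Fisher's exact test. For the long-term data, SAP 10.3.3.2 counts subjects meeting the same criteria and adds: "A listing of all subjects with any laboratory determination meeting OMERACT criteria of Grade 3 or 4 will be provided by Grade".

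**Grades.** In SAP Appendix A, creatinine Grade 2 is "> 1.5 – 3.0 × Baseline; > 1.5 – 3.0 × ULN", and Grade 3 starts above 3.0 × baseline or 3.0 × ULN. CPK Grade 2 is above 2.5 and up to 5.0 × ULN, and Grade 3 starts above 5.0 × ULN. The protocol's Appendix N footnote has the same Grade 2 and Grade 3 limits.

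**Action limits, protocol Table 7.**
- Creatinine above 1.5 × baseline and above ULN: "repeat the test for serum creatinine (with subject in an euvolemic state) to confirm the results". Then: "If the results of the repeat testing still meet this criterion, then interrupt study drug". A re-start rule follows.
- Confirmed creatinine of 2 mg/dL or more: interrupt, again with a re-start rule.
- Confirmed CPK of 4 × ULN or more without symptoms: the subject may stay on drug at the investigator's discretion. At that level and "accompanied by symptoms suggestive of myositis or rhabdomyolysis, interrupt study drug and contact AbbVie TA MD".
- All of these call for a supplemental renal or CPK eCRF.

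**Status.** Protocol 6.1.1.3 names "Increased serum creatinine and renal dysfunction" and elevated CPK among the adverse events of special interest.

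**The concern.** The clinically significant table is where the SAP compares dose groups on laboratory abnormalities, and the 10.3.3.2 listing is the long-term laboratory record of individual subjects. For creatinine and CPK both start above the level at which the protocol itself acts or asks for extra data. A dose-related rise in creatinine that leads to interruptions could then show as no clinically significant values in that table and listing. Comparing safety across the three doses and placebo is a Period 1 objective, and long-term safety is a Period 2 objective. Period 2 runs until Japanese approval, so most exposure is collected there.

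**Working it through.** No figure in the plan needs reproducing; the check compares cut-offs.

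**Inputs.** Action limits are from protocol Table 7 and grades from SAP Appendix A. The two creatinine criteria within a grade (baseline, ULN) are read as alternatives. The documents give neither the laboratory's creatinine ULN nor subjects' baselines; I assume ULN 0.8–1.2 mg/dL and baseline (BL) 0.5–1.1 mg/dL.

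**1. CPK.** Values of 4, 4.5 and 5 × ULN are Grade 2; 5.01 × ULN is Grade 3. CPK from 4.0 to 5.0 × ULN reaches the Table 7 level and is not counted.

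**2. Creatinine, relative limit.** Ratios to baseline of 1.51, 2 and 3 are Grade 2; 3.01 is Grade 3. A subject interrupted under this rule is uncounted while creatinine is no more than 3.0 × BL and no more than 3.0 × ULN.

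In mg/dL, interruption starts at min(max(1.5 × BL, ULN), 2.0) and counting starts above min(3 × BL, 3 × ULN):

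| ULN | BL | Interrupt from | Count above | Uncounted width |
|---|---|---|---|---|
| 0.8 | 0.5 | 0.80 | 1.50 | 0.70 |
| 0.8 | 0.7 | 1.05 | 2.10 | 1.05 |
| 0.8 | 0.9 | 1.35 | 2.40 | 1.05 |
| 0.8 | 1.1 | 1.65 | 2.40 | 0.75 |
| 1.0 | 0.5 | 1.00 | 1.50 | 0.50 |
| 1.0 | 0.7 | 1.05 | 2.10 | 1.05 |
| 1.0 | 0.9 | 1.35 | 2.70 | 1.35 |
| 1.0 | 1.1 | 1.65 | 3.00 | 1.35 |
| 1.2 | 0.5 | 1.20 | 1.50 | 0.30 |
| 1.2 | 0.7 | 1.20 | 2.10 | 0.90 |
| 1.2 | 0.9 | 1.35 | 2.70 | 1.35 |
| 1.2 | 1.1 | 1.65 | 3.30 | 1.65 |

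Every pair leaves a band, 0.3 to 1.65 mg/dL wide. The ratio of counting level to interruption level runs from 1.50/1.20 = 1.25 to 2.10/1.05 = 2.0.

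**3. Creatinine, absolute limit.** A value of 2 mg/dL exceeds 3 × a reference only if that reference is below 2/3 = 0.667 mg/dL. If baseline and ULN are both at least about 0.67, 2 mg/dL is below Grade 3 and uncounted (2.5 × at 0.8, 1.67 × at 1.2: both Grade 2). With baseline 0.6 it is 3.33 × baseline, Grade 3, and counted.

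**4. Other Table 7 limits.** Haemoglobin below 8 g/dL, ANC below 1000, WBC below 2000, platelets below 50,000 and ALT/AST above 3 × ULN start in Grade 3. A haemoglobin fall of 3.0 g/dL and ALC below 500 reach Grade 4. Apart from rounding at the edges, only creatinine and CPK have action limits in Grade 2. Liver tests also have their own threshold tables (SAP 10.3.2.4, 10.3.3.3).

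**5. Where else a Grade 2 value can appear.**

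| Output | Shows it? |
|---|---|
| Period 1 shift tables (SAP 10.3.2.2) | Yes, as Grade 2, but not isolated: CPK Grade 2 pools values below and above 4 × ULN, and creatinine Grade 2 includes values above 1.5 × baseline that are not above ULN |
| Long-term shift table | None in SAP 10.3.3, although protocol 8.1.5.1 and 8.1.5.3 call for grade shift tables with safety analysed for both periods combined |
| Mean change by visit | Only as part of a mean |
| TEAE tables by preferred term | Only if reported as an adverse event |
| AESI tables (SAP Table 13) | CPK under one preferred term; renal under a narrow acute renal failure query |

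**The case against.** The strongest reply is that the SAP does not ignore Grade 2. Period 1 shift tables cover all four grades. The protocol commits to grade shift tables and to analysing both periods together, and the SAP says it elaborates the protocol's methods. All reported treatment-emergent events are tabulated by preferred term, as percentages in Period 1 and as rates long term. Protocol 6.1.1.1 links laboratory adverse events to the Section 6.1.7 criteria. Nothing obliges a clinically significant threshold to equal a dosing precaution; Grade 3–4 is a prespecified convention.

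Most of this stands, and it limits the point to a small one. It does not close the gap. The shift tables do not separate out the Table 7 limits, the long-term shift table is missing from the SAP, and adverse event status is not automatic for an interruption that has a re-start rule.

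Stronger readings that a reader might infer are not supported:
- That the SAP counts only Grade 3–4 laboratory values anywhere. This is true of the clinically significant counts and the long-term listing only.
- That drug is permanently stopped for creatinine. Table 7 interrupts and re-starts.
- That every such interruption is missed. Creatinine above 3 × baseline or 3 × ULN is counted.
- That CPK of 4 × ULN alone interrupts drug. Symptoms are required, and only 4–5 × ULN is uncounted.
- That counting always starts at twice the interruption level. The ratio depends on baseline and ULN.

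**Conclusion.** The point holds in limited form. Creatinine above 1.5 × baseline and above ULN, up to 3.0 × baseline and 3.0 × ULN, triggers interruption once confirmed but is left out of the clinically significant counts and the long-term listing. So is creatinine of 2 mg/dL or more while it stays within 3 × both references, and so is CPK of 4–5 × ULN. The comparison of relative thresholds needs no distributional assumption. The widths in mg/dL rest on the assumed baselines and ULNs, and the reading of the grade criteria as alternatives is mine. The documents give no distribution of peak creatinine or CPK, so I put no number on the subjects affected. The gap matters more in the long-term analysis, where the SAP plans no shift table. Severity: minor.

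**What to change.** - Keep the Grade 3–4 counts in SAP 10.3.2.3 and 10.3.3.2.
- In both sections add the number, percentage and a listing of subjects meeting each Table 7 limit: creatinine above 1.5 × baseline and above ULN; creatinine of 2 mg/dL or more; CPK of 4 × ULN or more. Use the same treatment groups as the existing tables, and state whether a row counts any value or only confirmed ones.
- Carry the protocol's Grade 1–4 shift table into SAP 10.3.3.

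This follows what the SAP already does for liver tests. No clinical limit changes. The cost is SAP wording, three rows in each of two tables, the listings and one shift table. The central laboratory data and supplemental eCRFs are already collected. The creatinine and CPK safety figures may look slightly less favourable.

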### **8.1.5            Safety Analyses**

#### **8.1.5.1            General Considerations**

Safety analyses will be carried out using the Safety Analysis Set. Analyses will be conducted for Period 1 alone, as well as for Period 1 and Period 2 combined. Safety analyses are based on treatments actually received. Safety will be assessed by AEs, physical examination, laboratory assessments, ECG, and vital signs. Frequency tables and lists of subjects with treatment-emergent AEs by preferred term as in the Medical Dictionary for Regulatory Activities (MedDRA) dictionary, by system organ class, by severity, and by relationship to the study drug as assessed by the Investigator will be provided. The changes from baseline in vital signs, physical examination results, and clinical laboratory values will be analyzed in a descriptive manner. Shift of laboratory values from baseline to defined time points will be tabulated.

Missing safety data will not be imputed.

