10.3 Analysis of Laboratory Data

10.3.1 Variables and Units

All laboratory parameters to be collected in this study are listed below. Laboratory parameters will be reported using the standard international (SI) units.

Table 14. List of Laboratory Variables

Laboratory Variables
Hematology
White Blood Cell (WBC) Count
Red Blood Cell (RBC) Count
Hemoglobin
Hematocrit
Platelets count
Neutrophils
Basophils
Eosinophils
Lymphocytes
Monocytes
Bands

Table 14. List of Laboratory Variables (Continued)

Laboratory Variables

Chemistry

Total Bilirubin
Alkaline Phosphatase (ALP)
Serum glutamic oxaloacetic transaminase (SGOT/AST)
Serum glutamic pyruvic transaminase (SGPT/ALT)
Total Protein
Albumin
Glucose
Triglycerides
Blood Urea Nitrogen (BUN)
Creatinine
Uric acid
Sodium
Potassium
Calcium
Inorganic Phosphorus
Creatine Phosphokinase (CPK)
Chloride
Bicarbonate
Cholesterol
LDL cholesterol
HDL cholesterol
International Normalized Ratio (INR) reflux only

Urinalysis

Specific Gravity
pH
Protein
Glucose
Ketones
Blood
Microscopic Examination (if needed)
Urobilinogen

Table 14. List of Laboratory Variables (Continued)

Laboratory Variables
Urinalysis (continued)
Bilirubin
Leukocytes
Nitrites
Other
hs-CRP
QuantiFERON-TB Gold
IgG and IgM
ESR

10.3.2 Analysis of Laboratory Data for Period 1

The laboratory data will be summarized by the "as treated" treatment groups (Upadacitinib 7.5 mg QD, Upadacitinib 15 mg QD, Upadacitinib 30 mg QD, and combined placebo groups) and overall.

10.3.2.1 Assessment of Mean Change from Baseline and Mean Percentage Change from Baseline in Clinical Laboratory Variables

Analyses of mean change from baseline in continuous hematology, chemistry, and urinalysis variables which are measured longitudinally will be performed by visits and by "as treated" treatment group. For each change from baseline analysis, the following summary statistics will be presented for each treatment group: sample size, baseline mean, visit mean, and the mean, standard deviation, and median of the changes from baseline. An ANOVA model with treatment as a factor will be used to test statistical significance for the change from baseline mean among different treatment groups.

In addition, similar analyses will be conducted for mean percentage change from baseline in hemoglobin, NK cells, LDL, HDL and triglycerides.

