10.3.2.2 Assessment of Shift from Baseline in Clinical Laboratory Variables

The baseline and post-baseline laboratory observations will be categorized as Grade 1, Grade 2, Grade 3, and Grade 4 according to OMERACT criteria (Rheumatology Common Toxicity Criteria v.2.0). For creatine phosphokinase, creatinine, NCI CTC criteria will be used.

For each laboratory variable, shift tables will be generated that cross tabulate the subjects' as deemed appropriate by "as treated" treatment group:

- Category of the baseline value versus category of the final value,
- Category of the baseline value versus maximum category.
- Category of the baseline value versus minimum category.

Note that the minimum/maximum category is used, rather than the category of the minimum/maximum value. The two may be different due to variation in the reference range.

No statistical tests will be performed for this analysis.

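### Lipid profile change is a protocol AESI, but the laboratory shift and clinically-significant outputs use a grading scale with no lipid row

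*SAP*

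**What the plan says.** Protocol 6.1.1.3 names "Lipid profile changes" among the AESIs to be monitored. Protocol Table 5 and SAP Table 14 include cholesterol, "LDL cholesterol", HDL cholesterol and triglycerides.

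On shifts, protocol 8.1.5.1 states: "Shift of laboratory values from baseline to defined time points will be tabulated". SAP 10.3.2.2 sets the scale: "The baseline and post-baseline laboratory observations will be categorized as Grade 1, Grade 2, Grade 3, and Grade 4 according to OMERACT criteria", with one exception: "For creatine phosphokinase, creatinine, NCI CTC criteria will be used". The same section continues: "For each laboratory variable, shift tables will be generated", qualified by wording that allows some judgement about which are appropriate. Protocol 8.1.5.3 uses the same grading scheme.

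On clinically significant values, SAP 10.3.2.3 states: "The criteria for potentially clinically significant laboratory values will be determined by OMERACT criteria of Grade 3 or 4". SAP 10.3.3.2 applies the same criterion to the long-term counts and listing.

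For continuous summaries, SAP 10.3.2.1 and 10.3.3.1 give change from baseline by visit (mean, standard deviation, median). They add "mean percentage change from baseline in hemoglobin, NK cells, LDL, HDL and triglycerides".

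**The concern.** An AESI is a topic on which the reader of a safety report expects to see how many subjects were affected in each group. For lipids, the laboratory part of the plan has no rule that turns a measured value into a category. The SAP sets up shift tables variable by variable, but the chosen scale cannot produce one for lipids.

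At stake is a count by dose. Period 1 compares three doses with a combined placebo group of 48 (16 + 16 + 16), and comparing safety with placebo is a stated objective. As written, no laboratory table or listing would show how many subjects on each dose, against placebo, moved from a normal to an abnormal lipid value.

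**Working it through.** No arithmetic beyond counting is needed. The check is whether any planned laboratory output can classify a lipid value.

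**1. Rules that classify laboratory values**

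| Output | Section | Classification used |
|---|---|---|
| Shift tables, Period 1 | SAP 10.3.2.2 | OMERACT Grades 1-4; NCI CTC for CPK and creatinine |
| Clinically significant counts with Fisher's exact tests, Period 1 | SAP 10.3.2.3 | OMERACT Grade 3 or 4; same two exceptions |
| Long-term counts and listing | SAP 10.3.3.2 | OMERACT Grade 3 or 4; same two exceptions |
| Separate threshold counts | SAP 10.3.2.4, 10.3.3.3 | Liver tests only |

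**2. Rows of the scale.** SAP Appendix A and protocol Appendix N print the same laboratory rows:
- haematology K1-K5: 5 rows
- chemistry L1-L3 and L5-L16: 15 rows, covering calcium, glucose, potassium, sodium, CPK, uric acid, creatinine, AST, ALT, alkaline phosphatase, bilirubin and LDH
- urinalysis M1-M4: 4 rows

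That is 5 + 15 + 4 = 24 rows, of which 0 grade a lipid. The numbering skips L4 in both documents. What L4 held cannot be told from the text, but no lipid criterion is printed.

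**3. Result for the four lipids.** Cholesterol, LDL, HDL and triglycerides: 0 of 4 can receive a grade. So 0 of 4 can enter any of the first three outputs in the table, and the fourth does not concern them.

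**4. The AESI route.** SAP Table 13 has 16 categories, 0 of them for lipids. The AESI list in protocol 8.1.5.2.1, which is not exhaustive, names none either.

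**5. What remains for lipids**
- By-visit mean, standard deviation and median of the change, for all four.
- Mean percentage change for LDL, HDL and triglycerides. Total cholesterol is not named.
- Adverse events. Under protocol 5.3.1.1 (Clinical Laboratory Tests), a value that leads to discontinuation of study drug or needs treatment is recorded as an adverse event. Protocol 6.1.1.1 agrees and adds values that the investigator considers to be adverse events. These are counted by system organ class and preferred term (SAP 10.2.2.2) and enter the long-term rates (SAP 10.2.3).
- Protocol 8.1.5.3 also plans change to minimum, maximum and final value. SAP 10.3.2.1 and 10.3.3.1 list by-visit change only, so it is unclear whether these will be produced.

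A lipid value that becomes abnormal but leads to no treatment, no discontinuation and no investigator report is therefore counted nowhere.

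**6. Is it a matter of document dates?** SAP version 1.0 (31 August 2017) predates the current protocol (23 February 2018). That does not explain the gap. Protocol Appendix O shows that lipid changes were already on the superseded AESI list, and the current protocol 8.1.5.3 relies on the same scale.

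**The case against.** The best defence is that lipids were handled deliberately, as continuous data. LDL, HDL and triglycerides are three of only five variables singled out for percentage change. The protocol says that AESIs are monitored, not that each will be tabulated by category. The shift-table rule leaves room to omit variables for which a table is not appropriate. This has weight: it shows that lipids were not forgotten. But it supplies no lipid category, and nowhere does the SAP say that this AESI is assessed through continuous summaries. The sponsor also adapted the scale elsewhere: NCI CTC for CPK and creatinine, an edited alkaline phosphatase row, and separate liver thresholds.

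The objection also rules out some stronger readings.

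- A reader might infer that no subject with abnormal lipids will be counted anywhere. The documents do not support this, because lipid changes that need treatment must be recorded as adverse events and are then counted. The gap concerns counts from laboratory values.
- A reader might infer that group summaries would hide a few large rises. The planned median and standard deviation would help to reveal such a pattern, although they give no count of abnormal subjects.
- A reader might infer that Period 2 means are biased toward no effect by lipid-lowering drugs and that the medication data go unused. Such drugs are not on the prohibited list, so some attenuation is possible. But the documents give no rate of use, concomitant medications are tabulated by generic name (SAP 6.3), and the protocol's change to maximum would keep a peak measured before treatment.
- A reader might call lipid change a known effect of the drug class. The available text does not say so, and the AESI listing is reason enough.

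**Conclusion.** The point holds for the laboratory analyses. Lipid change is a named AESI and four lipids are measured, yet 0 of 4 can be graded, 0 of 24 laboratory rows and 0 of 16 AESI search categories cover them, and three planned outputs (SAP 10.3.2.2, 10.3.2.3 and 10.3.3.2) are empty for them. What is lost is the count, by dose against placebo, of subjects whose lipids became abnormal without this being recorded as an adverse event. How many subjects that would be cannot be estimated from the documents.

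The conclusion assumes that the printed appendices are the scale to be used and that the unprinted L4 row is not a lipid row. It affects no efficacy result, eligibility rule or treatment decision. The SAP should be changed because the remedy is cheap and the topic is one the protocol itself selected.

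**What to change.** - **SAP 10.3.2.2:** classify cholesterol, LDL, HDL and triglycerides as low, normal or high by the central-laboratory reference range. Tabulate baseline category against maximum post-baseline category (minimum for HDL) by treatment group. The section already plans baseline-to-minimum and baseline-to-maximum comparisons, so the layout exists.
- **SAP 10.3.2.3 and 10.3.3.2:** report the number and percentage of subjects who move from normal to abnormal for each lipid, labelled as reference-range shifts so that they are not read as Grade 3-4 values.
- **SAP 10.3.2.1 and 10.3.3.1:** carry over change to minimum, maximum and final value from protocol 8.1.5.3.
- **SAP 10.2.2.6:** state that the lipid AESI is assessed through these tables.

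Reference-range classification is workable here. Protocol Appendix O shows that the superseded text of 8.1.5.3 applied it to all laboratory data. The cost is SAP wording and a few extra safety tables, with no new data.

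An analysis that stops follow-up when lipid-lowering medication starts should not be added. It would tend to remove the subjects with the largest rises and could increase the bias it is meant to reduce.

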4.0 Study Objectives, Design and Procedures

4.1 Objectives

Period 1

1. To confirm dose response in the efficacy of Upadacitinib 7.5 mg QD, 15 mg QD and 30 mg QD, and to compare the efficacy of Upadacitinib versus placebo for the treatment of signs and symptoms of Japanese subjects with moderately to severely active RA who are on a stable dose of csDMARDs and have an inadequate response to csDMARDs.
2. To compare the safety and tolerability of Upadacitinib 7.5 mg QD, 15 mg QD and 30 mg QD versus placebo in Japanese subjects with moderately to severely active RA who are on a stable dose of csDMARDs and have an inadequate response to csDMARDs.

Period 2

To evaluate the long-term safety, tolerability, and efficacy of Upadacitinib 7.5 mg QD, 15 mg QD and 30 mg QD in subjects with RA who have completed Period 1.

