4.3 Sample Size

Sample size was estimated based on the previous global Phase 2 trial (Study M13-537). Assuming an ACR20 response rate of 46% for placebo group, 62% for low dose group (7.5 mg QD), 68% for middle dose group (15 mg QD) and 80% for high dose group (30 mg QD) of Upadacitinib, the sample size to have 90% power and two-sided alpha of 5% to detect a statistically significant dose-response using Cochran-Armitage test will be 42 subjects per group. And the sample size to demonstrate the superiority of Upadacitinib compared to placebo will be 46 subjects to provide the 90% power and 5% of two-sided alpha. Taking 5% of drop-out rate into consideration, sample size will be 48 per group (total sample size: 192 subjects).

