10.2.2.1 Adverse Events Overview

The number and percentage of subjects experiencing TEAEs will be summarized by "as treated" treatment group and overall for the following AE categories.

- All TEAEs
- Treatment-emergent serious adverse events (SAEs)
- Treatment-emergent severe adverse events
- TEAEs reasonably possibly related to study drug
- TEAEs of special interest
- TEAEs leading to discontinuation of study drug
- TEAE leading to death

Additional AEs may be considered for tabulation/summary based on recommendations from Clinical and Safety as deemed appropriate.

For TEAEs of special interest, the point estimate and 95% CI (using normal approximation) will be provided for the treatment difference in AE percentage between each Upadacitinib dose group and the combined placebo group.

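### Grade 3-4 laboratory values get counts and percentages but no difference or confidence interval, and Fisher p-values above 0.100 are suppressed

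*SAP*

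**What the plan says.** Period 1 has a comparative safety objective. SAP 4.1 opens it with "To compare the safety and tolerability of Upadacitinib 7.5 mg QD" and goes on to the two higher doses, all against placebo.

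For laboratory values of potential clinical significance, SAP 10.3.2.3 sets out four things:

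- Event: "The criteria for potentially clinically significant laboratory values will be determined by OMERACT criteria of Grade 3 or 4", with NCI CTC grades for CPK and creatinine.
- Descriptive output: "The number and percentage of subjects meeting the criteria for potentially clinically significant laboratory values will be summarized by" as-treated group and overall. No filter applies to this.
- Comparison: "Comparisons of the percentage of subjects experiencing a value meeting the criteria between treatment groups will be performed using Fisher's exact tests". Neither sidedness nor a pairwise or overall form is stated.
- Display: "Only p-values ≤ 0.100 when rounded to three digits will be presented".

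No difference between groups and no interval is planned there. SAP 10.2.2.1 handles adverse events of special interest differently: a point estimate and 95% CI "will be provided for the treatment difference in AE percentage between" each dose and combined placebo, with no display threshold.

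**The concern.** The display rule depends on the result. A comparison that falls short of p = 0.100 loses its only inferential summary, and nothing takes its place. The reader is left with two percentages and no statement of precision, in the analysis where precision matters most: small groups, few events, and a stated aim of comparing safety with placebo.

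Other Period 1 laboratory output does not fill the gap. The shift tables in SAP 10.3.2.2 carry no tests, the liver thresholds in 10.3.2.4 are frequencies only, and the ANOVA in 10.3.2.1 concerns mean change rather than Grade 3-4 events.

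The intervals for events of special interest cover it only in part. Under Protocol 6.1.1.1 a laboratory abnormality is an adverse event only if it leads to discontinuation, needs medical intervention, or the investigator judges it to be one. A Grade 3-4 value can therefore count in 10.3.2.3 and never reach 10.2.2.1.

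**Working it through.** **Group size.** The only size calculation concerns ACR20. SAP 4.3 says the superiority sample "will be 46 subjects to provide the 90% power and 5% of two-sided alpha". For 80% v 46% the pooled mean is 0.63, and the uncorrected size is

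n = [1.960 × √(2 × 0.63 × 0.37) + 1.282 × √(0.46 × 0.54 + 0.80 × 0.20)]² / 0.34² = 40.3, so 41.

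With the continuity correction, n/4 × [1 + √(1 + 4/(0.34n))]² = 45.95, so 46, which matches the SAP. Then 46/0.95 = 48.4, stated as 48 per group. Combined placebo is 16 + 16 + 16 = 48. No power is stated for any laboratory comparison.

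**Assumptions.** Two-sided Fisher, each dose against combined placebo, 48 v 48. The documents give no Grade 3-4 rates, so true rates are varied over a range.

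**Smallest count that produces a p-value.** With 0/48 on placebo, the two-sided p for x/48 on a dose is 2 × C(48,x)/C(96,x):

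- x = 4: 2 × 194,580/3,321,960 = 0.117, suppressed.
- x = 5: 2 × 1,712,304/61,124,064 = 0.056, shown.

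Enumerating the other tables gives:

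| Placebo events | Fewest dose events for a displayed p |
|---|---|
| 0 | 5 (10.4%) |
| 1 | 7 (14.6%) |
| 2 | 8 (16.7%) |
| 3 | 10 (20.8%) |

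**Chance that the p-value is displayed.** Sum the product of the two binomial probabilities over all 49 × 49 outcomes with p, rounded to three digits, at or below 0.100:

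| Assumed placebo v dose | Shown | Blank |
|---|---|---|
| 0% v 8% | 0.34 | 0.66 |
| 0% v 10% | 0.53 | 0.47 |
| 2% v 10% | 0.295 | 0.705 |
| 2% v 12% | 0.44 | 0.56 |
| 2% v 15% | 0.64 | 0.36 |
| 5% v 15% | 0.37 | 0.63 |
| 5% v 20% | 0.64 | 0.36 |

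**What the suppressed results would have said.** The Newcombe interval combines the Wilson limits of the two proportions. For 4/48 the Wilson limits are 3.3% and 19.6%; for 0/48 they are 0% and 7.4%. So

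- lower limit = 8.3 - √[(8.3 - 3.3)² + 7.4²] ≈ -0.6 points
- upper limit = 8.3 + (19.6 - 8.3) = 19.6 points

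| Dose v placebo | p (suppressed) | Difference, points | Newcombe 95% CI |
|---|---|---|---|
| 3/48 v 0/48 | 0.242 | 6.2 | -2.2 to 16.8 |
| 4/48 v 0/48 | 0.117 | 8.3 | -0.6 to 19.6 |
| 6/48 v 1/48 | 0.111 | 10.4 | -0.6 to 22.7 |
| 7/48 v 2/48 | 0.159 | 10.4 | -1.8 to 23.4 |

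The normal approximation that SAP 10.2.2.1 uses would give 0.5 to 16.2 for 4/48 v 0/48. It excludes zero where Newcombe does not, so it should not be carried over to counts this small.

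**If one four-group test is meant.** Simulation (2,000 trials per pattern; rates in order placebo, 7.5, 15, 30 mg) displays a p-value more often than most of the pairwise cases above: 0.61 for 0/3/5/10%, 0.48 for 1/3/5/10%, 0.60 for 1/10/10/10% and 0.86 for 0/0/0/10%.

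**The case against.** The strongest reply is that nothing is hidden. Counts and percentages appear for every group whatever the p-value, so 0/48 v 4/48 prints as 0% v 8.3% and anyone can derive the difference and an interval. That stands. A reader might infer that such a harm appears as no result at all, and 10.3.2.3 does not support that reading: only the p-value is withheld, and only a planned measure of precision is missing.

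Second, a reader might infer that the plan treats a blank as evidence of no difference. Neither document says so. Protocol 8.1.5.1 describes laboratory analysis as descriptive, and no alpha or safety conclusion hangs on these tests.

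Third, reserving intervals for prespecified events of special interest is a legitimate reporting choice. Other adverse events and vital signs get counts and percentages only, and 0.100 is a looser flag than 0.05. This is fair: the contrast with 10.2.2.1 is not an error. It shows only that the better method is already in use in the same document.

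Fourth, the rates are assumed, and pairwise testing is assumed. Both are correct and limit the size of the point. Placebo rates need not be near zero: entry excludes lymphocyte counts below 800/µL, while Grade 3 lymphopenia covers 500 to 900/µL, so a subject may enter at Grade 3.

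Finally, low power at 0.05 comes from the sample size. Printing p = 0.117 would not change it, so power is not an argument against the display rule.

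**Conclusion.** The point holds in a limited form. For Grade 3-4 laboratory values, SAP 10.3.2.3 adds to the counts only a p-value that is displayed selectively, and it plans no estimate of the difference or its precision. If the tests are two-sided and pairwise at 48 v 48, the p-value is often blank for excesses of about 10 points or less over a low placebo rate (about 70% for 2% v 10%, 47% for 0% v 10%). It is mostly shown for larger ones (64% for 2% v 15%).

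A reader might go further and say that material harms will usually go unreported. The documents do not support that. The counts are always there, the frequency of blanks depends on rates the documents do not give, and an overall four-group test would display more often.

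This is a cheap improvement to reporting. It does not affect the validity of the efficacy analysis.

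**What to change.** In SAP 10.3.2.3:

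- For each upadacitinib dose against combined placebo, present the risk difference with a two-sided 95% confidence interval suited to small counts (Newcombe, score or exact), for every laboratory variable with at least one event.
- Delete the 0.100 display rule. Either drop the Fisher p-values or show all of them, labelled descriptive.
- State that the comparisons are pairwise against combined placebo, and that they are two-sided.

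The cost is SAP wording and some added columns in a table already planned, with no new data or subjects. The drawback is a longer table in which some intervals will be wide; that width is the information now missing.
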